4.5 Justification for Dosing Regimen

A standard 1 mL volume of administration will be used for all treatment groups. Note that 2 ml injections are a routine intra-articular dose volume in current medical practice.

4.6 Population to be Studied

About 270 adult participants with a diagnosis of moderate to severe pain due to osteoarthritis of the knee will be enrolled in this study.

4.7 Statement of Compliance

This study will be conducted in compliance with the protocol, Good Clinical Practice (GCP), the ethical principles of the Declaration of Helsinki, and applicable regulatory and Institutional Review Board (IRB), Human Research Ethics Committee (HREC) or Independent Ethics Committee (IEC) requirements.

5.0 STUDY PURPOSE AND OBJECTIVES

The purpose of this study is to gather evidence for the safety, tolerability, and efficacy of XT-150 as a treatment for pain associated with OA.

- The primary objective of this study is to confirm the safety and tolerability of a single intra-articular dose of XT-150.
- The secondary objective is to establish the analgesic efficacy of a single intraarticular dose of XT-150 as a treatment for pain in participants with OA of the knee.

6.0 STUDY DESIGN

6.1 Description of the Study

This is a Phase 2 safety, tolerability, and efficacy study of XT-150 in adult participants with pain due to osteoarthritis of the knee. The study will be conducted in 2 Stages, A and B.

Stage A is placebo controlled for six months following intra-articular injection in the Index Knee, which is defined by Kellgren-Lawrence grading and participant-reported pain. The primary efficacy endpoint is 30% response rate in WOMAC pain at Day 180.

Stage B continues for an additional six months of safety and efficacy monitoring during which participants can elect for a second injection to the Index Knee. Active 150 μ g or 450 μ g XT-150 will be randomly chosen for the second injection.

Participants will provide informed consent and meet all study eligibility criteria before any study procedures are initiated. FAST (Appendix 4: Focused Analgesia Selection Test) will be used to select patients who reliably report the magnitude of thermal stimulations.

Baseline confirmation of study eligibility will be completed within one day preceding study drug administration. Study drug will be administered by intra-articular (IA) injection into the joint space of the knee.

About 270 participants will be randomly enrolled into 1 of 3 treatment groups (approximately 90 participants/group). Treatment Groups:

- 1. Placebo (1 mL)
- 2. 150 μg XT-150 (1 mL)
- 3. 450 μg XT-150 (1 mL)

The study will be conducted in 2 stages, A and B:

- A. Placebo controlled for 6 months
- B. Continued follow up for 6 months with the option of randomly receiving a single 150 μg or 450 μg injection as the second injection to the Index Knee (knee dosed in Stage A).

Safety parameters and efficacy endpoints for each participant will be evaluated monthly for about 1 year from the first XT-150 dose (Stage A, Day 0)

The Schedules of Assessments and Procedures are presented in Table 1 and Table 2. Day 0 is defined as the day of study drug administration. Subsequent study days are defined by the number of consecutive calendar days after drug administration.

6.2 Follow up Assessments

All participants will be assessed for physical examination findings and vital signs following signing of the informed consent form (ICF) and for AEs and SAEs, throughout the study for each treatment group.

Serum samples will be collected from all participants to test for the presence of anti-IL-10 antibodies. Samples will be analyzed using a validated assay by an independent, central bioanalytical laboratory. Procedures for collection, storage, and shipping of immunogenicity samples are described in the study Lab Manual.

Efficacy assessments will be performed at the screening visit (WOMAC Pain Score for eligibility), then all measures at Baseline, on Day 7, Day 30, and approximately monthly thereafter for up to 1 year. Efficacy endpoints will be evaluated at each study visit and overall.

A telephone call documenting safety and efficacy assessments may be used for participants unable to physically attend follow up visits due to COVID-19 infection or corona virus exposure concerns. Home services may be employed for blood collections.

6.3 Number of Participants

About 270 participants will be treated and evaluated.

Expected Duration of Subject Participation

Subject participation will require a commitment of approximately 1 year of safety, tolerability, and efficacy evaluation. In addition, a screening visit will occur up to 30 days before enrollment.

Baseline assessments for study eligibility will be completed within one day before study drug administration. Day 0 is defined as the day of study drug administration. Subsequent study days are defined by the number of consecutive calendar days thereafter.

Follow-up visits will occur on Study Day 7, Study Day 30, and approximately monthly thereafter.

6.5 Method of Treatment Assignment and Blinding

After informed consent has been obtained, participants will be screened for study eligibility before enrollment.

In Stage A, participants will be randomly enrolled into one of 3 groups, two XT-150 treatment groups (150 μg or 450 μg) or placebo.

At any time in Stage B up to Day 330, inclusive, participants can elect for a single injection to the knee dosed in Stage A (Index Knee). The second injection dose will be randomized to be either 150 μ g or 450 μ g XT-150. There will be no placebo comparator in Stage B.

Instructions for study drug preparation and dosing are given in Section 8.0.

7.0 SELECTION, DISCONTINUATION, AND WITHDRAWAL OF PARTICIPANTS

To be enrolled in this study, all participants must meet all of the following inclusion criteria and none of the exclusion criteria.

7.1 Participant Inclusion Criteria

Participants are required to meet ALL of the following inclusion criteria:

- 1. Symptomatic disease due to osteoarthritis, defined as a WOMAC Pain score ≥ 8 (worst possible = 20)
- 2. Focused Analgesia Selection Test (Analgesic Solutions, Wayland, MA) will be used to determine whether patients can report pain with sufficient consistency to enter the clinical trial (See Appendix 4)
- 3. Males and females between 45 and 85 years of age, inclusive.
- 4. Kellgren-Lawrence grading of 2 or 3 within the last 6 months (See Appendix 5)
- 5. Stable analgesic regimen during the 4 weeks prior to enrollment.
- 6. In the judgment of the Investigator, acceptable general medical condition
- 7. Life expectancy >6 months
- 8. Male and female participants who are heterosexually active and not surgically sterile must agree to use effective contraception, including abstinence, for the duration of the study.
- 9. Have suitable knee joint anatomy for intra-articular injection
- 10. Willing and able to return for the follow-up (FU) visits
- 11. Able to read and understand study instructions, and willing and able to comply with all study procedures

7.2 Participant Exclusion Criteria

Participants must NOT meet any of the following exclusion criteria:

- 1. Hypersensitivity, allergy, or significant reaction to any ingredient of the study drug, including double-stranded DNA,
- 2. Previously received XT-150 injection(s)
- 3. Scheduled partial or complete knee replacement within 6 months; participant agrees not to schedule a knee replacement during Stage A of the study
- 4. History of knee arthroplasty on the Index Knee selected for study injection(s)
- 5. History of rheumatoid arthritis or other inflammatory disease
- 6. History of immunosuppressive therapy; systemic steroids in the last 3 months
- 7. Received knee injection with hyaluronic acid or stem-cells in the last 6 months
- 8. Knee injection of glucocorticoid in the last 3 months
- 9. Current treatment with systemic immunosuppressive (systemic corticosteroid therapy or other strong immunosuppressant)
- 10. Currently receiving systemic chemotherapy or radiation therapy for malignancy
- 11. Clinically significant hepatic disease as indicated by clinical laboratory results ≥3 times the upper limit of normal for any liver function test (e.g., aspartate aminotransferase, alanine aminotransferase)
- 12. Severe anemia (Grade 3; hemoglobin <8.0 g/dL, <4.9 mmol/L, <80 g/L; transfusion indicated), Grade 1 white cell counts (lymphocytes <LLN 800/mm³; <LLN 0.8 x 10⁹ /L, neutrophils <LLN 1500/mm³; <LLN 1.5 x 10⁹ /L)
- 13. Positive serology for human immunodeficiency virus, hepatitis B virus, or hepatitis C virus

- 14. Significant neuropsychiatric conditions; dementia, major depression, or altered mental state that in the opinion of the Investigator will interfere with study participation
- 15. Current treatment with systemic antibiotics or antivirals (EXCEPTION: topical treatments)
- 16. Current anticoagulant or anti-platelet treatment (e.g., warfarin, heparins, factor X inhibitors, clopidogrel, prasugrel, ticagrelor, or dipyridamole). Low-dose (≤ 325 mg/day) aspirin is permitted.
- 17. Known or suspected history of active alcohol or intravenous/oral drug abuse within 1 year before the screening visit
- 18. Use of any investigational drug or device within 3 months before enrollment or current participation in a trial that included intervention with a drug or device; or currently participating in an investigational drug or device study
- 19. Any condition that, in the opinion of the Investigator, could compromise the safety of the participant, the participant's ability to communicate with the study staff, or the quality of the data

7.3 Requalification for Entry

Participants not fulfilling the entry criteria and not treated may be rescreened for participation if their eligibility characteristics have changed.

7.4 Participant Withdrawal Criteria

7.4.1 Withdrawal from Study Protocol

Participants on study drug who wish to withdraw completely from this clinical study should be encouraged to complete the assessments for Day 360/Termination. However, participants may withdraw consent to participate in this study at any time without penalty or loss of benefits to which the participant is otherwise entitled. Every reasonable effort should be made to determine the reason a participant withdraws prematurely, and this information should be recorded on the appropriate page(s) of the case report form (CRF). Participants may be withdrawn from the study for any of the following reasons and will be captured in CRFs:

- Participant unable or unwilling to continue
- Participant's perceived lack of benefit
- Participant elects to withdraw informed consent
- Due to an adverse event
- Protocol non-compliance
- Participant is lost to follow up
- The PI considers that it is in the participant's best interest not to continue participation in the study

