7.4.2 Early Discontinuation from Study Drug Administration

Since the study treatment consists of a single dose of XT-150, and the participants should qualify for treatment before enrollment, no participants are anticipated to need to discontinue study drug unless they develop an SAE or need for excluded medications in the 24 hours prior to dosing.

NOTE: The Medical Monitor should be contacted to discuss whether to continue with planned XT-150 dosing in the event that the participant situation changes significantly in the 24 hours prior to XT-150 injection such that participant safety is at risk.

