8.0 STUDY DRUGS

[figure not shown]
Participants will be randomly enrolled into placebo or XT-150 (150 µg, or 450 µg) groups and will receive a single, 1 mL intra-articular injection on Day 0 of Stage A. Participants may receive a second injection (of either 150 µg or 450 µg) in Stage B.

Table 4. Final Drug Product Quantitative Composition Per Vial

Ingredient	Function	Target Amount per Vial
plasmid DNA	Active ingredient	150 μg/mL or 450 μg/mL

Protocol XT-150-2-0204

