10.7 Adverse Event Follow-up

All unresolved SAEs ("ongoing" at discharge) will be followed by the study staff until resolution or deemed stable.

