13.5.2 Statistical methods for the binary outcomes

Whether the subject achieves at least a 30% improvement from baseline in WOMAC Pain Score at Day 180 will be coded as a binary outcome: responder or non-responder. Subjects who withdraw from study before Day 180 or otherwise do not provide a response at that time point will be considered non-responders. The response outcome will be analyzed in a logistic regression model with treatment as the main factor and baseline WOMAC pain as a covariate. Within this model, z-tests will be used to compare the two XT-150 doses to placebo, with step-down Dunnett-like adjustments for multiplicity of doses. Handling of special cases, such as zero responders in a treatment group, will be addressed in the SAP.

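### Protocol 7.4.1 lets dosed participants leave the whole study for an adverse event, non-compliance or perceived lack of benefit, and no rule keeps those who still consent in follow-up, so obtainable safety and Day 180 data are lost

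*Protocol*

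**What the plan says.** Protocol 7.4.1, on withdrawal from the study, says: "Participants may be withdrawn from the study for any of the following reasons and will be captured in CRFs". Seven reasons follow. Consent withdrawal and loss to follow-up have their own entries. Adverse event, protocol non-compliance and perceived lack of benefit are listed beside them, so these three can apply to people who could still be followed. A participant who wishes to leave "should be encouraged to complete the assessments for Day 360/Termination".

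Protocol 7.4.2 deals with stopping study drug. It begins "Since the study treatment consists of a single dose of XT-150" and says that "no participants are anticipated to need to discontinue study drug unless they develop an SAE" or need an excluded medication in the 24 hours before dosing. It is silent on the period after the injection. Section 8.0 adds that "Participants may receive a second injection" in Stage B.

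On follow-up, Protocol 13.4 plans AE collection from consent to Day 360. Section 10.7 says that unresolved SAEs "will be followed by the study staff until resolution or deemed stable", and has no counterpart for non-serious events. Section 6.2 allows a telephone assessment, which "may be used for participants unable to physically attend follow up visits due to COVID-19 infection or corona virus exposure concerns".

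On efficacy, Protocol 13.5.2 states: "Subjects who withdraw from study before Day 180 or otherwise do not provide a response at that time point will be considered non-responders". SAP 9.3 applies the same outcome to any subject without a Day 180 response. The continuous endpoints go into a repeated-measures model without imputation (Protocol 13.5.3). Section 7.5 does not replace withdrawn participants, and section 13.1 makes no allowance for dropout.

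**The concern.** In a trial of repeated dosing, leaving because of an adverse event at least ends exposure. Here, up to Day 180, the exposure has already happened in full. Withdrawal from the study on the three grounds changes nothing about treatment in that period and only ends data collection. After Day 180 the one remaining treatment decision is the optional second injection, and a participant can go without it and stay in the study. The protocol never separates stopping treatment from stopping follow-up.

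Two things are at stake. The primary objective is safety and tolerability, and a participant who leaves because of an adverse event is the one whose later course is most informative. The primary efficacy endpoint counts a missing Day 180 score as a failure, so a participant who would have given a score, and might have been a responder, is counted against the arm.

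**Working it through.** **Safety follow-up.** AE collection is planned to Day 360. A participant withdrawn for a non-serious AE at Day 30 (an illustration) loses up to 360 − 30 = 330 days of it. What remains is an encouraged termination assessment and, if an SAE is open, follow-up under 10.7.

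**Inputs for the primary endpoint.** n = 90 per arm, response 10% on placebo and 30% on each dose, stated power 95% for at least one dose and 85% for both (Protocol 13.1 and Table 7). Familywise one-sided alpha is 0.025 over two doses (13.5.1), with step-down Dunnett-like z-tests in a logistic model (13.5.2). The simulation omits the baseline covariate. Critical values are 2.212 for the larger statistic (Dunnett, correlation 0.5) and then 1.96. The share d lost before Day 180 is an assumption.

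**Statistic.** For each dose against placebo, z = [logit(pT) − logit(pC)] / √(1/xT + 1/(n − xT) + 1/xC + 1/(n − xC)), where x is the number of responders.

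**Reproducing the stated power.** The plain logit test gives 96.2% / 87.6%, so the figure for both doses is 2.6 points above the stated 85%. Adding 2 successes and 2 failures to every arm gives 95.3% / 84.5%, and all 12 cells of Table 7 then agree within 1.1 points. That this is how Table 7 was made is an inference: SAP 9.3 mentions such an addition only for an arm with no responders.

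**Effect of avoidable loss.** If loss is unrelated to response, observed rate = true rate × (1 − d). At d = 3% the rates are 0.10 × 0.97 = 9.7% and 0.30 × 0.97 = 29.1%. At d = 10% they are 9% and 27%. In people, d = 10% is 9 per arm, of whom 9 × 0.30 = 2.7 would have responded on a dose and 9 × 0.10 = 0.9 on placebo.

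| Avoidable loss per arm | Both doses, plain logit | Both doses, Table 7 match | At least one dose, Table 7 match |
|---|---|---|---|
| 0 | 87.6% | 84.5% | 95.3% |
| 3% | 86.0% | 82.6% | 94.5% |
| 10% | 81.5% | 77.4% | 92.0% |

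SAP section 10 drops the step-down. With 2.212 required for each dose, the Table 7 match gives 77.2% for both doses with no loss and 68.6% at d = 10%.

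**Unequal loss (Table 7 match, rates assumed).**
- No true difference, 30% response everywhere, 15% lost on placebo and 5% on each dose: observed rates are 0.30 × 0.85 = 25.5% and 0.30 × 0.95 = 28.5%. One-sided familywise error is about 5.7%, against 2.1% with no loss and 2.5% nominal.
- True 10% and 30%, with 5% lost on placebo and 15% on each dose: observed rates are 9.5% and 25.5%. Power is 84.4% for at least one dose and 64.2% for both.

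**The case against.** The strongest case against has five parts.

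*The list is permissive and partly the participant's own doing.* This stands. Perceived lack of benefit usually starts with the participant, and the study is double-blind. A reader might infer that sites can decide part of the primary endpoint by removing people. The documents do not show that: only non-compliance, the investigator's judgement and perhaps an adverse event are site-initiated, in unknown number.

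*Safety follow-up does not simply end.* This stands. Section 10.3 asks for a date of resolution or stabilization for every AE, the synopsis requires repeated contact attempts after missed visits, and discontinuations due to AEs are reported to the ethics bodies (10.4). None of these sets a contact schedule after withdrawal or covers events that begin later.

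*No observed score is overwritten.* A reader might take the rule to replace Day 180 scores with failures. It does not: SAP 9.3 applies only where no response was given, and only the binary endpoint is affected. Section 9.0 also lets an out-of-window visit be rescheduled. The loss is of scores that could have been collected and were not.

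*Withdrawal can affect exposure.* It does rule out the Stage B injection. That injection is optional, so forgoing it does not require leaving the study.

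*The power figures overstate the gain.* Largely right. Consent withdrawals and losses to follow-up would remain, so only the avoidable share counts. People who leave for lack of benefit are often true non-responders, for whom imputation costs little. It is also conjecture that XT-150 would cause more AE withdrawals: Protocol 4.3 reports mild injection-site reactions and no XT-150-related SAE.

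**Conclusion.** The point holds in a limited form. Followed as written, the plan allows follow-up to stop for dosed participants who still consent, on grounds that end no treatment before Day 180. It thereby gives up safety data and some Day 180 outcomes that could have been obtained.

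The size is uncertain because the documents give no withdrawal rate. For an avoidable loss of 3% to 10% in every arm, power for both doses falls by about 2 to 7 points on the Table 7 basis, or about 2 to 6 on the plain logit basis. With equal loss in each arm, these are upper bounds as long as those who leave respond no more often than those who stay. Unequal loss is a separate matter: it biases the comparison in either direction, and the error rate of about 5.7% depends on the assumed split of 15% against 5%. The documents do not support the stronger readings that safety follow-up is abolished, that recorded scores are discarded, or that the trial loses its power through this clause.

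**What to change.** In Protocol 7.4.1, state that an adverse event, a protocol deviation or perceived lack of benefit is not by itself a reason to end follow-up, and that participants who still consent continue scheduled assessments to Day 360 whether or not they receive a second injection. Keep consent withdrawal, loss to follow-up and the investigator's best-interest ground; the last protects participants and should not be removed.

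In sections 6.2 and 9.0, allow the existing telephone option, for KOOS and AEs, for anyone who would otherwise miss Day 180. Extend 10.7 to AEs that led to withdrawal. Keep non-response for scores that are still missing. SAP 9.3 needs no change, since it already turns on whether a Day 180 response was given.

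The change concerns data collection only and leaves dosing untouched. It costs protocol wording, some extra telephone contacts, and a few scores taken by telephone instead of on site.

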7.4.2 Early Discontinuation from Study Drug Administration

Since the study treatment consists of a single dose of XT-150, and the participants should qualify for treatment before enrollment, no participants are anticipated to need to discontinue study drug unless they develop an SAE or need for excluded medications in the 24 hours prior to dosing.

NOTE: The Medical Monitor should be contacted to discuss whether to continue with planned XT-150 dosing in the event that the participant situation changes significantly in the 24 hours prior to XT-150 injection such that participant safety is at risk.

7.5 Replacement of Participants

After randomization, withdrawn participants will not be replaced.

7.6 Study Termination by Sponsor and Termination Criteria

The Sponsor reserves the right to terminate an investigational site or this clinical study at any time. Reasons for termination may include, but are not limited to, the following:

- The incidence or severity of AEs in this or other studies of XT-150 indicate a
 potential health hazard to participants
- Serious or persistent noncompliance by the Investigator with the protocol, clinical research agreement, or applicable regulatory guidelines in conducting the study
- HREC/IRB decision to terminate or suspend approval for the investigation or the Investigator
- Investigator request to withdraw from participation
- Participant enrollment is unsatisfactory

8.0 STUDY DRUGS

[figure not shown]
Participants will be randomly enrolled into placebo or XT-150 (150 µg, or 450 µg) groups and will receive a single, 1 mL intra-articular injection on Day 0 of Stage A. Participants may receive a second injection (of either 150 µg or 450 µg) in Stage B.

Table 4. Final Drug Product Quantitative Composition Per Vial

Ingredient	Function	Target Amount per Vial
plasmid DNA	Active ingredient	150 μg/mL or 450 μg/mL

Protocol XT-150-2-0204

